9.0 Statistical Considerations

Subjects who are overweight or obese (n=20) will be recruited through this IRB. To analyze study hypotheses, and for comparison to normal weight individuals, we will share data from the study cohort of [name] (IRB #151943). This will include identical data acquired from at least n=20 subjects who are normal weight (18 to <25 kg/m²) and who meet identical inclusion/exclusion criteria.

Statistical analysis procedures for Aim 1: Statistical analyses will be performed by key study personnel and members of the Center for Quantitative Sciences at the VUMC. The primary statistical objective of Aim 1 is to test the hypothesis that adults who are salt sensitive have higher baseline tissue sodium relative to adults who are not salt sensitive. To test this, we will divide participants into those who are salt sensitive (SS, ≥5 mmHg change in mean arterial pressure ΔMAP following high salt diet compared to low salt diet) or not salt sensitive (NSS, <5 mmHg ΔMAP), according to a review of methods and recommendations from Kurtz et al.²⁶. The metric ΔMAP represents a continuous variable of SSBP. A Mann Whitney U test will be applied to determine whether tissue sodium content is significantly different in SS and NSS groups. Based on a prior study of tissue sodium storage in adults who are hypertensive (n=10)

or normotensive (n=12)¹⁹ we anticipate a similar difference in tissue sodium of 6±4 (mean ± standard deviation, mmol/L) between SS and NSS adults. Our study is designed to provide at least 80% power to detect differences in tissue sodium with a two-sided significance of p<0.05.

Our secondary statistical objective of Aim 1 is to test the hypothesis that tissue sodium content and potential risk factors for SSBP, including biological sex, age, and tissue fat/water fraction as a sensitive surrogate of BMI, are related to Δ MAP as a continuous variable. We will apply multivariable regression analysis using tissue sodium, fat/water fraction, biological sex, and age as independent variables, and Δ MAP as the dependent variable among all participants. With a sample size of 40 , we should be able to evaluate the four predictors of Δ MAP (each with one degree of freedom) without over-fitting the model.

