(see mentor support letter). The primary statistical objective of Aim 1 is to test the hypothesis that adults who are salt sensitive have elevated baseline tissue sodium relative to adults who are not salt sensitive. To test this, we will apply a previously-published, informed cutoff to dichotomize participants into those that are salt sensitive (SS, ≥ 5 mmHg reduction in Δ BP depletion) or salt resistant (SR, < 5 mmHg reduction in Δ BP), according to a review of methods and recommendations from Kurtz *et al.*¹¹. The metric Δ BP represents a continuous variable of SSBP; tests for normality and homoscedasticity will be made. Depending on normality, a Mann Whitney U test or a Student's t-test will be applied to determine whether muscle sodium content is significantly different in SS and SR groups, matched for race and accounting for biological sex as a covariate. Based on a prior study of tissue sodium storage in adults with hypertension (n=10) and normotensive (n=12)²⁶ we anticipate a similar difference in tissue sodium of 6 ± 4 (mmol/L) between SS and SR adults. With a sample size of 20 in each group, our study design will provide at least 80% power to detect differences in tissue sodium with a two-sided significance of $p<0.05$.

Our secondary statistical objective of Aim 1 is to test the hypothesis that muscle sodium content and potential risk factors for SSBP, including biological sex and tissue fat/water fraction as a sensitive surrogate of BMI, are related to Δ BP as a continuous variable. We will apply multivariate regression analysis using muscle sodium, fat/water fraction, and biological sex as independent variables, and Δ BP as the dependent variable among all participants. With a sample size of 40, we will have sufficient power to evaluate three predictors of Δ BP at the

Statistical analysis procedures for Aim 2:

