The primary statistical objective of Aim 2 is to test the hypothesis that tissue sodium content is elevated in tissues affected by impaired lymphatic flow. To test this hypothesis, the same statistical considerations outlined in Aim 1 will be applied. Next, we will calculate either the Pearson's- r or Spearman's-rho correlation coefficient, depending on normality, between lymphatic flow velocity and tissue sodium content in adults who are SS or SR and matched for age, biological sex, and BMI. The correlation coefficient and adjusted p-values and 95% confidence intervals will be reported for each test, with the hypothesis that the relationship will be significant in SS but not SR individuals. Based on our preliminary data in normotensive black women who display a Spearman's-rho=0.49 between tissue sodium and fat/water fraction (**Table 1**), we anticipate a similar or greater correlation with lymphatic function; with 16 subjects in each group, our design will provide 80% power to detect a correlation with two-sided significance of $p<0.05$ between tissue sodium content and lymph flow velocity. To test whether the relationship between lymphatic flow velocity and muscle sodium is unique for the different groups, a linear regression with robust errors and an interaction term will be applied. The covariates will be biological sex and fat/water fraction. The coefficient for the interaction will be quantified as the difference between the slopes.

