Statistical analysis procedures for Aim 3: The primary statistical objective of Aim 3 is to test the hypothesis that elevated tissue sodium content is associated with reduced renal perfusion in adults with SSBP. To test this hypothesis, we will calculate either the Pearson's- r or Spearman's-rho correlation coefficient, depending on normality, between renal cortical perfusion and peripheral tissue sodium content in adults who are SS or SR and matched for age, race, and BMI, and accounting for biological sex as a covariate. The correlation coefficient and adjusted p-values and 95% confidence intervals will be reported for each test. Based on our preliminary data in normotensive black women who display a Spearman's-rho=0.49 between tissue sodium and fat/water fraction (**Table 1**), we anticipate a similar or greater correlation with renal perfusion; with 20 subjects in each group, our design will provide 80% power to detect a correlation with two-sided significance of $p<0.05$ between tissue sodium content and renal cortical perfusion. Next, to compare the relationships in the SS group between i) tissue sodium and lymph flow velocity and ii) tissue sodium and renal cortical perfusion, a linear regression for each relationship with robust errors and an interaction term will be applied. The covariates will be biological sex and fat/water fraction. The coefficient for the interaction will be quantified as the difference between the slopes.

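### SAP 6.1 checks for equal variances but does nothing with the result, so Student's t on muscle sodium can miss its 5% level if the SS and SR groups differ in both size and spread

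*SAP*

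**What the plan says.** SAP 6.1 (Aim 1) splits participants at a 5 mmHg blood-pressure response into SS and SR and compares their muscle sodium. The checks are introduced in a sentence about the blood-pressure measure: ΔBP "represents a continuous variable of SSBP; tests for normality and homoscedasticity will be made". The rule for muscle sodium follows directly, "tests for normality and homoscedasticity will be made. Depending on normality, a Mann Whitney U test", and names both options: "Depending on normality, a Mann Whitney U test or a Student's t-test will be applied". The SAP gives no test or threshold for either check and does not say what follows if variances are unequal. The same sentence asks for biological sex as a covariate.

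The SAP plans 20 per group with at least 80% power at a two-sided 5% level. The effect size is given as "we anticipate a similar difference in tissue sodium of 6", with ±4 mmol/L; protocol 9.0 labels the ±4 as a standard deviation. No SD is given for each group.

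Other places that bear on this:
- Protocol 9.0 fixes the Mann-Whitney U test for this comparison, with no preliminary check.
- SAP 9 plans residual plots for regression models but attaches no action to them.
- SAP 9.1, on the primary analysis, still holds template text and names no test.
- Robust errors are planned only for the interaction regressions in Aims 2 and 3.

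**The concern.** Student's t pools the two variances. With unequal group sizes, the pooled standard error is dominated by the larger group. If the smaller group is the more variable one, the standard error is too small and the test rejects too often. If the larger group is the more variable one, the test is too conservative and loses power. A homoscedasticity check would be the natural place to catch this, but the SAP's rule does not use its result.

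Group sizes here are not under the trial's control, because SS/SR status is an outcome of the diet periods and not an allocation. At stake is the p-value for the primary objective of Aim 1.

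**Working it through.** **Inputs.** 40 participants; difference 6 and SD 4 mmol/L; two-sided 5% (SAP 6.1, protocol 9.0). Prevalence of salt sensitivity: at most 50% in normotensive adults and 74% in black American adults (SAP 4.1, protocol 1.0). SD ratios of 1.5 and 2 are my assumptions.

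**The plan's own figure.** For 20 per group, difference 6 and SD 4, the noncentral t distribution gives 99.6% power. The stated minimum of 80% is met.

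**Plausible splits.** 0.50 × 40 = 20, so up to 20 SS, or about 20:20. 0.74 × 40 = 29.6 SS and 10.4 SR, or about 30:10. If 74% applied, the chance of 18 to 22 SS participants among 40 would be 0.7%.

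**Large-sample check.** Let k² be the variance that Student's t assumes for the mean difference, divided by the true variance:

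k² = [(n₁s₁² + n₂s₂²)/(n₁ + n₂)] × (1/n₁ + 1/n₂) ÷ (s₁²/n₁ + s₂²/n₂)

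Type I error ≈ 2[1 − Φ(1.96k)].

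- 30 SS with SD 4, 10 SR with SD 8: assumed variance 28 × 0.1333 = 3.733; true variance 0.533 + 6.4 = 6.933; k = 0.734; error 15.0%.
- 30 SS with SD 8, 10 SR with SD 4: assumed 52 × 0.1333 = 6.933; true 2.133 + 1.6 = 3.733; k = 1.363; error 0.8%.
- Equal SDs, or equal group sizes: k = 1; error 5.0%.

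**Simulation.** Normal data, equal means, 200,000 runs per cell. In each unequal-SD cell, the first figure is for the larger group more variable and the second for the smaller group more variable. At 20:20 the two cases are mirror images.

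| Split | SD ratio | Student's t | Welch's t |
|---|---|---|---|
| 30:10 | 1 | 5.0% | 5.1% |
| 30:10 | 1.5 | 1.8% / 10.7% | 5.0% / 5.1% |
| 30:10 | 2 | 0.9% / 15.4% | 5.0% / 5.1% |
| 25:15 | 1.5 | about 3% / 8% | 5.0% / 5.0% |
| 25:15 | 2 | about 2.4% / 9.5% | 5.0% / 5.1% |
| 20:20 | 1.5 | 5.1% | 5.0% |
| 20:20 | 2 | 5.2–5.3% | 5.0% |

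**Does it matter which variable is checked?** I simulated the whole two-stage rule (Shapiro-Wilk at 5%, then the chosen test) at 30:10 with a twofold ratio. With the check on ΔBP the error is 0.9% and 15.2%; with the check on sodium within groups it is 1.0% and 15.3%. The location of the check makes no practical difference.

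**Alternatives.** Mann-Whitney at 30:10 with a twofold ratio runs at 2.0% and 9.4%, so the protocol's test is only a partial remedy. A linear model on SS status and sex with HC3 errors runs at about 4% to 6% at 30:10 across these SD ratios, with sex balanced within groups.

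**Power after the change.** At 30:10 with difference 6 and a common SD of 4, Welch's t has 96.9% and Student's t about 98% (97.9% by the noncentral t).

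**The case against.** The strongest reply is that the error rates rest on two assumptions. The SAP plans 20:20, where Student's t is sound. Hypertension is an exclusion, so the figure for normotensive adults may fit this population better than the 74%, which is not limited to normotensives. The documents give a single SD, and unequal sizes alone do no harm: at 30:10 with equal SDs the error is 5.0%. All of this stands. It makes the size conditional, but it does not give the homoscedasticity check a consequence.

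Three stronger readings are tempting, and the documents do not support them.

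- *The check is made on the wrong variable, and this distorts the error rate.* ΔBP is the only variable named beside the checks, but the sentence is ambiguous. The next sentence is about sodium, and ΔBP is itself the outcome of the secondary regression, so checking it has a purpose. In any case the error rate is the same for either variable.
- *The documents imply a 30:10 split and therefore an invalid test.* They support a range of splits, and they say nothing about unequal spread or its direction.
- *Aims 2 and 3 should use Spearman throughout.* The SAP does choose the "correlation coefficient, depending on normality, between lymphatic flow velocity and tissue sodium content", and likewise for renal perfusion in Aim 3. No error rate has been worked out for that choice, and the slope comparisons there already use robust errors.

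**Conclusion.** The point holds in a limited form. The SAP plans a variance check that cannot change the analysis, and it keeps an equal-variance test for groups whose sizes are not fixed by design. No other section repairs this.

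The consequence ranges from nil (20:20, or equal SDs) to a type I error of 0.9% to 15.4% (30:10, twofold SD ratio). Inflation arises only if the smaller group is the more variable one; in the opposite case the test is conservative. These figures assume normal data and SD ratios that the documents do not give, so they show sensitivity and are not a forecast. A change is still worth making, because a better test is available at almost no cost and the stated 80% power survives it. The unnamed variable beside the checks is a separate matter of wording with no effect on these figures.

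**What to change.** In SAP 6.1 (Aim 1), replace the normality-driven choice with one test named in advance: Welch's unequal-variance t-test on muscle sodium. If sex is kept as a covariate, which neither currently named test can handle, use instead a linear model of muscle sodium on SS status and sex with HC3 standard errors. Name Mann-Whitney as the sensitivity analysis. If any distributional check is kept for description, state that it is made on muscle sodium within each group and does not select the test.

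Reconcile this with protocol 9.0, which fixes Mann-Whitney, so that both documents name the same primary test. Leave the correlation choices in Aims 2 and 3 as they are on this ground.

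Cost: wording changes in the SAP and the protocol, and about one percentage point of power at 30:10 when variances are equal. No new data are needed.

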4.1 Preface

Salt sensitive blood pressure preferentially affects black Americans

Salt sensitive blood pressure (SSBP) is a physiologic phenotype defined by a parallel change in blood pressure in response to dietary salt load. SSBP is fundamentally related to the body's inability to clear salt, leading to elevated blood pressure and a life-long increased risk of cardiovascular disease. SSBP was determined to be an independent risk factor for developing cardiovascular disease in hypertensive patients almost two decades ago¹, and more recently SSBP was found to portend all-cause mortality². It is a prevalent condition that affects up to 50% of normotensive, 75% of hypertensive³, 74% of black American adults⁴, and is estimated to be 6% more prevalent among females than males^{5, 6}. Black Americans are preferentially affected by this phenotype and represent one of the most at-risk population for cardiovascular diseases related to SSBP. Salt sensitivity is increased with the occurrence of metabolic syndrome associated with abdominal obesity⁷ and insulin resistance⁸. Current tests for SSBP require dietary salt loading, are time-intensive and, more importantly, provide limited mechanistic information on the incompletely characterized mechanisms of tissue salt storage.

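### Aim 2 of the SAP words its hypothesis as significance in salt-sensitive but not salt-resistant participants, which does not test a difference, and the planned interaction test is not made decisive

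*SAP*

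**What the plan says.** SAP section 6.1, under the Aim 2 procedures, first sets an objective about raised sodium where lymphatic flow is impaired and applies the Aim 1 methods to it. It then plans a Pearson or Spearman correlation between flow velocity and tissue sodium in the SS and SR groups, "with the hypothesis that the relationship will be significant in SS but not SR individuals". On reporting: "The correlation coefficient and adjusted p-values and 95% confidence intervals will be reported for each test". The adjustment method is not named.

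The only Aim 2 sample-size statement concerns these within-group correlations: "with 16 subjects in each group, our design will provide 80% power to detect a correlation" at the two-sided 5% level. The assumed size comes from another pair of variables, "Spearman's-rho=0.49 between tissue sodium and fat/water fraction".

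The paragraph then adds a second analysis. It begins "To test whether the relationship between lymphatic flow velocity and muscle sodium is unique for the different groups" and describes a linear regression with robust errors, a group interaction, and sex and fat/water fraction as covariates. The difference in slopes is the estimate. No power is given for it, the type of robust variance is not named, and nothing says which of the two analyses settles the Aim 2 conclusion.

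Protocol section 9.0 says for Aim 2 that the sodium–flow relation depends on salt sensitivity. Its model, however, has flow velocity, ΔMAP, sex and age as main effects, with no interaction term.

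**The concern.** A correlation that reaches significance in one group and misses it in the other can come from limited power or unequal group sizes when the relation is the same in both. A non-significant SR result does not show that the relation is absent.

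Salt sensitivity is known only after the diets, from a 5 mmHg cut-off, so the group sizes are not under design control. If SR is the smaller group, its correlation is the more likely to miss significance whatever the biology.

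At stake is the claim that a link between lymphatic flow and sodium storage is particular to salt-sensitive people. As worded, the Aim 2 hypothesis would be met by the pattern alone, even with an interaction estimate near zero.

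**Working it through.** **Inputs**
- Correlation 0.49, two-sided 5%, 16 per group (SAP 6.1, Aim 2). Only the magnitude matters for power, so the expected inverse direction changes nothing.
- 20 per group (SAP 6.1, Aim 1: "With a sample size of 20 in each group"); total 40.
- SS share: SAP 4.1 gives up to 50% of normotensive adults and "74% of black American adults". Of 40, 50% gives 20:20; 74% gives 29.6, about 30:10.

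**Step 1: the plan's own power figure**

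Power(r, n) = Φ(atanh(r)·√(n−3) − 1.96), with atanh(0.49) = 0.536.
- n = 16: 0.536 × √13 = 1.933; Φ(−0.027) = 0.489
- n = 20: 0.536 × √17 = 2.210; Φ(0.250) = 0.599
- n = 30: 0.536 × √27 = 2.785; Φ(0.825) = 0.795
- n = 10: 0.536 × √7 = 1.418; Φ(−0.542) = 0.294

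The stated 80% at 16 per group does not reproduce; the result is about 49% (simulated: Pearson 51%, Spearman 45%). For 80%, n = ((1.960 + 0.842)/0.536)² + 3 = 30.3, so 31 per group, or 32 with the Spearman variance factor of 1.06.

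**Step 2: the pattern when both groups share one correlation**

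The groups are independent, so P(SS significant, SR not) = power(SS) × [1 − power(SR)].

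| SS:SR | r = 0.30 | r = 0.49 | r = 0.60 | r = 0.70 |
|---|---|---|---|---|
| 16:16 | 16% | 0.489 × 0.511 = 25% | 21% | 11% |
| 20:20 | 19% | 0.599 × 0.401 = 24% | 15% | 5% |
| 30:10 | 32% | 0.795 × 0.706 = 56% | 52% | 37% |
| 10:30 | 8% | 0.294 × 0.205 = 6% | 2% | 0.3% |

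Simulation at r = 0.49 gives 24.6%, 23.5% and 55.8% for the first three splits. At r = 0 the figure is 0.05 × 0.95 = 4.75%. With equal groups the probability is p(1 − p), which cannot exceed 25%. A power near 50% puts the plan close to that ceiling. If the unnamed adjustment were Bonferroni over the two groups (an assumption), the r = 0.49 figures would still be about 24–25% and 56%.

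**Step 3: the planned interaction under the same null**

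The model was simulated with identical slopes at r = 0.49: normal data, sex and fat/water fraction unrelated to sodium or flow, and 6,000 runs per split.

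| SS:SR | Interaction p < 0.05, HC3 | Interaction p < 0.05, HC1 | Pattern and interaction, HC3 | Pattern and interaction, HC1 |
|---|---|---|---|---|
| 16:16 | 4.0% | 7.9% | 1.7% | 3.4% |
| 20:20 | 3.9% | 7.3% | 1.6% | 3.0% |
| 30:10 | 4.4% | 10.3% | 2.0% | 4.9% |

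So when the pattern is false, the interaction usually does not support it, and the SAP gives no rule for that conflict.

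**Step 4: power of the interaction for 0.49 versus 0**

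Fisher z approximation: Φ(0.536/SE − 1.96), with SE = √[1/(n₁−3) + 1/(n₂−3)].
- 16:16: SE 0.392; Φ(−0.593) = 28%
- 20:20: SE 0.343; Φ(−0.397) = 35%
- 30:10: SE 0.424; Φ(−0.696) = 24%

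This approximates the covariate-adjusted model; it is not that model's exact power.

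**The case against.** The strongest reply is that the SAP already contains the right test. The interaction stands in the same paragraph and is aimed at exactly this question. Order in a paragraph is not hierarchy, and the text says only that correlations will be reported, with a predicted pattern attached. This stands to a large extent. A reader might infer that the plan rests on the two p-values alone; it does not. What remains is that the hypothesis as written is a statement about significance in each group, the sole power statement serves that reading, and nothing ranks the two analyses.

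A reader might also take 24–56% as the plan's general false-claim rate. It is not. It assumes r = 0.49, borrowed from sodium and fat/water fraction, and an SS share of 50–74%. The upper end needs the 74% figure, although SAP 4.1 also gives up to 50% for normotensive adults and the study excludes hypertension. If SS were the smaller group, the pattern would be uncommon.

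Finally, a reader might extend the point to Aim 3, which also computes SS and SR correlations. The SAP states no such pattern there. Its hypothesis concerns adults with salt-sensitive blood pressure, for whom the SS correlation is a direct test. Its interaction compares the lymphatic and renal relations within SS. Calling the SS correlation descriptive would remove Aim 3's primary test.

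**Conclusion.** The concern holds for the wording of Aim 2 in the SAP. The stated pattern is not evidence that the relation differs by salt sensitivity. With a common correlation of 0.49 it arises in about one trial in four at 16 or 20 per group, and in about 56% at 30:10. The figure is smaller for clearly weaker or stronger correlations and under 5% at zero. These results assume independent groups, bivariate normal data and the Fisher approximation, which the simulations support.

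The documents do not support saying that the plan lacks a valid test, since the interaction is prespecified. The defect is that two analyses that will often disagree are left unranked, with the invalid one carrying the hypothesis and the sample-size argument. The remedy is small, but it should be in place before the data are analysed.

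**What to change.** In the Aim 2 text of SAP 6.1:
- Delete significance in SS but not SR as the hypothesis criterion.
- State that dependence on salt sensitivity is concluded only from the interaction estimate (difference in slopes) with its 95% CI and p-value.
- Name a small-sample robust variance such as HC3. Simulated false-positive rates were about 4%, against 7–10% with HC1.
- Report the SS and SR correlations with confidence intervals as descriptive, and say that a non-significant SR result is not read as absence of a relation.
- State the interaction's approximate power (28% at 16:16, 35% at 20:20, 24% at 30:10, for 0.49 versus 0), and correct the 80% claim for 16 per group.

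In protocol section 9.0, align the Aim 2 model with its objective, for instance by adding the interaction between flow and salt sensitivity.

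Leave the SS correlation as Aim 3's primary test in the SAP. Protocol section 9.0 says that the renal relation, too, depends on salt sensitivity. If Aim 3 is to claim that, add an SS-versus-SR interaction there.

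The cost is text in both documents and no new data. The real price is a less favourable claim: the valid test is weak at this sample size, and Aim 2's only sample-size statement would then support descriptive results.

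### The 80% power stated for the Aim 2 and Aim 3 correlations does not follow from rho = 0.49: it is about 49% with 16 and 60% with 20 in a group

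*SAP*

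**What the plan says.** SAP section 6.1, Aim 2, plans a Pearson or Spearman correlation, chosen on normality, between lymphatic flow velocity and tissue sodium in SS or SR adults. The planning value is a Spearman rho of 0.49 between tissue sodium and fat/water fraction, from preliminary data in normotensive black women. From this the SAP says "we anticipate a similar or greater correlation with lymphatic function" and concludes that "with 16 subjects in each group, our design will provide 80% power to detect a correlation", at a two-sided 0.05 level.

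Aim 3 uses the same rho, level and power for renal cortical perfusion, but a different group size: "with 20 subjects in each group, our design will provide 80% power to detect a correlation".

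On what is tested, Aim 2 states its prediction "with the hypothesis that the relationship will be significant in SS but not SR individuals". Aim 3 is less explicit; its correlation is "between renal cortical perfusion and peripheral tissue sodium content in adults who are SS or SR". Both aims plan this reporting: "The correlation coefficient and adjusted p-values and 95% confidence intervals will be reported for each test". To compare the groups in Aim 2, "a linear regression with robust errors and an interaction term will be applied".

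Group membership is an outcome of the diet phase. Under Aim 1, "we will apply a previously-published, informed cutoff to dichotomize participants into those that are salt sensitive" or resistant. Protocol section 9.0 recruits by BMI: 20 overweight or obese participants here, and data on at least 20 normal-weight participants from a companion cohort.

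**The concern.** The same rho, significance level and power cannot require 16 in a group for one aim and 20 for the other, so at least one statement was not derived from 0.49. The check below shows that neither was, if the test is within a group.

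The error bears on how results are read. The Aim 2 hypothesis treats non-significance in SR as part of the expected pattern. At the planning value, a true within-group correlation would be missed about 51% of the time with 16 and 40% with 20, against the 20% that the SAP implies. A reader relying on the stated power could take a missed SR correlation as support for a mechanism specific to SS. A real SS correlation could equally be missed and dismissed.

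**Working it through.** **Inputs, all from SAP 6.1:** rho = 0.49; two-sided alpha = 0.05; n = 16 (Aim 2) and n = 20 (Aim 3) in each group; stated power 80% for both. Alpha is left unadjusted, which favours the SAP because it promises adjusted p-values without naming a method.

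**Attempt to reproduce the 80% (Fisher z).** Power ≈ Φ(atanh(rho)·√(n−3) − 1.960); the opposite tail is negligible. atanh(0.49) = 0.536.

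- n = 16: 0.536 × √13 = 1.933, power 48.9%
- n = 20: 0.536 × √17 = 2.210, power 59.9%

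Neither reproduces 80%.

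**Sample size for 80%.** n = ((1.960 + 0.842)/0.536)² + 3 = 30.3, so 31 in the tested group (power 81.0%).

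**Correlation detectable with 80% power.** rho = tanh(2.802/√(n−3)): 0.651 at n = 16 and 0.591 at n = 20.

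**Critical value.** With t on n−2 degrees of freedom, |r| must exceed 0.497 at n = 16 and 0.444 at n = 20. With 16 in a group, an observed Pearson r equal to the planning value would not reach p < 0.05.

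**Does the choice of test matter?** Simulated power under bivariate normality:

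| Planning value read as | n | Pearson test | Spearman test |
|---|---|---|---|
| Population Pearson 0.49 | 16 | 51% | 44% |
| Population Pearson 0.49 | 20 | 62% | 55% |
| Population Spearman 0.49 | 16 | 55% | 48% |
| Population Spearman 0.49 | 20 | 66% | 59% |

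A noncentral t calculation gives 55% and 66%. No two-sided within-group version comes near 80%. Partialling out sex, which Aim 3 calls for, uses √(n−4) and gives 57% at n = 20. If the p-value adjustment were Bonferroni over two tests (an assumption), Fisher z power would be 38% at n = 16 and 49% at n = 20.

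**Pooled reading.** With both groups in one test at rho = 0.49, n = 32 gives 82.3% (80.1% with a 1.06 variance factor for Spearman) and n = 40 gives 90.3% (88.6%).

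**Unequal groups.** Because SS and SR sizes are not fixed by design, these are illustrative splits of the planned minimum of 40 at rho = 0.49:

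| SS:SR | Power in SS | Power in SR |
|---|---|---|
| 10:30 | 29% | 79.5% |
| 15:25 | 46% | 71% |
| 20:20 | 60% | 60% |
| 25:15 | 71% | 46% |
| 30:10 | 79.5% | 29% |

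The smaller group always falls below the 60% that an equal split gives.

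**The case against.** The strongest defence is that a pooled test was meant and the group size only describes how the sample is made up. For Aim 2 the fit is close: 32 in total gives 80.1% to 82.3%. This may well be where the figure came from, and it would make the fault one of labelling. It does not settle the matter. The Aim 2 prediction of significance in one group but not the other needs separate tests, and for Aim 3 pooling gives about 90%, not 80%. Aim 3 has no such prediction, so there the ambiguity is real and the SAP should resolve it.

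A second defence is that a larger correlation was allowed for. But a value similar to 0.49 includes 0.49 itself, and neither 0.65 nor 0.59 is stated. Both aims cite a Table 1 that is not in the available text, so its contents cannot be checked.

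Third, Protocol section 9.0 analyses Aim 2 by regression among all participants with the continuous blood pressure change, and Aim 3 similarly. That is correct, so the miss rates above apply to the SAP's correlations only. The protocol gives no power figure for these aims that could support the SAP's 80%.

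Fourth, power in SS matters most, and the background sections cite salt sensitivity in up to 50% of normotensive and 74% of black American adults. Among 40 that suggests roughly 20 to 30 SS, with 60% to 79.5% power. This softens the concern for SS, but SR power then falls to between 60% and 29%, which makes a non-significant SR result harder still to interpret.

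Finally, the interaction test is not well powered either. For an assumed contrast of rho 0.49 against 0, a Fisher z difference, atanh(0.49)/√(2/(n−3)), gives about 28% at 16 and 35% at 20 per group. This stands as a limit on what Aim 2 can show. It does not favour comparing two p-values, because the interaction at least estimates the difference in question and gives its uncertainty.

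**Conclusion.** The concern holds. At the SAP's own planning value, within-group power is about 49% with 16 (44% to 55% across Pearson and Spearman versions) and about 60% with 20 (55% to 66%), not 80%. About 31 in the tested group would be needed. This rests on rho = 0.49 being the planning value, a two-sided unadjusted 0.05 level and a test within one group. Adjusting p-values or allowing for sex lowers the power further. If a pooled test was intended, the power is adequate at 0.49 but the wording is wrong, so the text needs correcting on either reading. The error affects how Aims 2 and 3 are interpreted; the Aim 1 comparison is not part of this point. It should be fixed.

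**What to change.** In SAP section 6.1, replace both 80% statements with text along these lines:

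*At rho = 0.49 and an unadjusted two-sided 0.05 level, power is about 49% with 16 and 60% with 20 subjects in a group (about 57% with 20 after partialling out sex). Power of 80% is available only for |rho| of at least about 0.65 and 0.59 respectively.*

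Then:

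- State for each aim whether the test is within group or pooled. If pooled, give the total (32 or 40) in place of the per-group number.
- Show power over SS:SR splits in both directions, from 10:30 to 30:10, labelled as illustrative.
- Keep the planned confidence intervals and interaction term. State that any Aim 2 SS-versus-SR conclusion rests on the slope difference and its confidence interval, not on significance in one group and its absence in the other.
- Add that a non-significant SR correlation is not evidence of no relationship.

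The cost is SAP wording and a less favourable stated power. No participants, data collection or new analyses are added. The emphasis of the Aim 2 conclusion moves to a test the SAP already plans.
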